**Left Ventricular Ejection Fraction**

A listing of the left ventricular ejection fraction results will be generated.

**ECOG Performance Status**

A summary of change from baseline in ECOG performance status by scheduled visits will be performed. Summaries will use frequency and percentage of subjects at each planned assessment time, best and worst-case post baseline.

A supporting listing will also be provided.

**Montreal Cognitive Assessment (MOCA)**

A listing of the Montreal Cognitive Assessment will be generated.

## 8. EFFICACY ANALYSES

All efficacy analyses will be based on the All Treated Subjects population unless otherwise specified. All analyses will be presented by dose of study treatment. Details of the planned displays are provided in [Appendix 10: List of Data Displays](#).

Response rate (RR) is defined as the percentage of subjects who achieved CR, CRp, PR or morphologic leukemia-free state (MLFS) among subjects who received at least one dose of treatment.

The investigator-assessed best response along with response rate (Without confirmation) will be summarized by dose of study treatment. A listing of investigator assessed responses (Without Confirmation) will be provided.

## 9. PHARMACOKINETIC ANALYSES

### 9.1. Primary Pharmacokinetic Analyses

Pharmacokinetic analysis will be the responsibility of the Clinical Pharmacology Modeling and Simulation (CPMS) Department, GSK.

The results of the pharmacokinetic analysis may be provided in a report separate from the main CSR.

#### 9.1.1. Endpoint / Variables

##### 9.1.1.1. Drug Concentration Measures

The GSK2879552 concentration-time data will be summarized by planned time point and dose cohort. Standard summary statistics will be calculated (i.e. mean, standard deviation, median, minimum and maximum). The ATRA concentration-time data will be listed.

Refer to [Appendix 5: Data Display Standards & Handling Conventions](#) (Section 11.5 Reporting Process & Standards).

##### 9.1.1.2. Derived Pharmacokinetic Parameters

Pharmacokinetic analysis of GSK2879552 will be conducted by noncompartmental methods using WinNonlin (Version 6.3 or higher). However pharmacokinetic analysis of ATRA will not be conducted due to the sample size limitations. The following pharmacokinetic parameters will be determined for if data permit:

Parameter	Parameter Description
AUC(0-t)	Area under the concentration-time curve from time zero to the time of the last quantifiable concentration (C(t)) will be calculated using the linear trapezoidal rule for each incremental trapezoid and the log trapezoidal rule for each decremental trapezoid.
$AUC(0-\tau)$	Area under the concentration-time curve during a dosing interval of duration "tau".
AUC (0-∞)	Area under the concentration-time curve extrapolated to infinity will be calculated as: $AUC = AUC(0-t) + C(t) / \lambda_z$ This will be calculated for Day 1 only
C max	Maximum observed plasma concentration, determined directly from the concentration-time data.
t max	Time to reach C max , determined directly from the concentration-time data.
t 1/2	Apparent terminal half-life will be calculated as: $t_{1/2} = \ln 2 / \lambda_z$
λ z	Apparent terminal phase elimination rate constant
C T	Trough concentration

To estimate the extent of accumulation after repeat dosing, the observed accumulation ratio (Ro) may be determined from the ratio of AUC(0- $\tau$ ) in Day 15/ AUC(0- $\tau$ ) in Day 1. The ratio of AUC(0- $\tau$ ) on Day 15/ Day 1 AUC(0- $\infty$ ) will be calculated to assess time invariance.

### 9.1.2. Population of Interest

The primary pharmacokinetic analyses will be based on the Pharmacokinetic population, unless otherwise specified.

### 9.1.3. Statistical Analyses / Methods

Details of the planned displays are provided in [Appendix 10](#): List of Data Displays and will be based on GSK Data Standards and statistical principles.

Unless otherwise specified, endpoints / variables defined in Section 9.1.1 will be summarised using descriptive statistics, graphically presented (where appropriate) and listed.

Plasma concentration-time data for GSK2879552 and ATRA will be listed by dose and Plasma concentration-time data for GSK2879552 will be summarized using descriptive statistics (n, mean, standard deviation [SD], median, minimum and maximum) by planned relative assessment time. Mean and/ or median values will be plotted over time. Individual plasma and urinary (if available) PK parameters values as well as a descriptive summary (mean, standard deviation, median, minimum, maximum, geometric mean, and the standard deviation, Coefficient of variance [CV]% and 95% confidence interval of log-transformed parameters, if applicable) by dose cohort will be reported. The following pharmacokinetic statistical analyses will only be performed, if sufficient data is available.

#### 9.1.3.1. Dose proportionality

If data permits, dose proportionality will be assessed using power model for:

- AUC(0- $\infty$ ) and Cmax on Day 1
- AUC(0- $\tau$ ) and Cmax on Day 15

Dose proportionality of GSK2879552 AUC(0- $\infty$ ) and Cmax following single dose administration and AUC(0- $\tau$ ) and Cmax following repeat dose administration will be evaluated using the power model as described below:

$$\log(\text{pharmacokinetic parameter}) = a + b * \log(\text{dose})$$

where a is the intercept and b is the slope.

The power model will be fitted by restricted maximum likelihood (REML) using SAS Proc Mixed. Both the intercept and slope will be fitted as fixed effects. If there is sufficient data, the model may also be fit with the intercept and/or slope as random effects depending on the ability of the model to converge and on estimation of variance-covariance matrix. The mean slope and corresponding 90% confidence interval will be estimated from the power model.

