1.4.4.2. Starting Dose

ATRA dose will be fixed at 45 mg/m²/day as two divided doses, as equally as feasible. The starting dose for GSK2879552 will be 2 mg. These starting doses were chosen based on the following considerations:

- GSK2879552 and ATRA do not have overlapping toxicity profiles based on the nonclinical toxicology and clinical safety profile of GSK2879552 at doses up to 4 mg daily.
- GSK2879552 mono-therapy has been well tolerated in this study at up to 4 mg daily dose. 2 mg daily dose of GSK2879552 represents a 50% reduction from the highest cleared dose of 4 mg daily as of 20-NOV-2015.
- A dose of 45 mg/m²/day for ATRA represents the recommended dose in APL as a single agent, well below the MTD of 150-215 mg/m²/day.
- The risk of GSK2879552 altering ATRA PK is low. In-vitro data suggests that GSK2879552 has a very low potential to inhibit or induce CYP enzymes, and to inhibit Pgp, BCRP, OATP1B1 or OATP1B3 transporters.
- The risk for ATRA to increase GSK2879552 exposure is very low. ATRA has only been reported to be an enzyme inducer.

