### 4. ANALYSIS POPULATIONS

Population	Definition / Criteria	Analyses Evaluated
Screened	
 
All subjects who were screened for eligibility
 
	
 
Screen Failure
 

Enrolled	
 
All participants who passed screening and entered the study.
 
	
 
Number of participants by Country and Siteid
 
Age Ranges
 

All Treated Subjects	
 
All randomized participants who received at least one dose of study treatment.
 
	
 
Study Pop, Safety, Efficacy
 

Pharmacokinetic	
 
All treated subjects for whom a PK sample is obtained and analysed.
 
	
 
PK
 

Pharmacodynamic	
 
All treated subjects who contribute to PD/Biomarker samples.
 
	
 
PD
 

Refer to [Appendix 10](#) List of Data Displays which details the population used for each display.

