## 5. CONSIDERATIONS FOR DATA ANALYSES AND DATA HANDLING CONVENTIONS

### 5.1. Study Treatment & Sub-group Display Descriptors

Code	Description	Data Displays for Reporting	
		Description	Order in TLF
A	GSK2879552	1mg QD	1
		2mg QD	2
		4mg QD	3
		8mg QD	4
		12mg QD	5
		20mg QD	6
		2mg QD/ATRA 45mg/m  /day	7
		20mg QD PK/PD EXPANSION	8

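### By default the dose-proportionality model takes in the 2 mg + ATRA subjects with no regimen term, so an ATRA effect on GSK2879552 exposure, if there is one, would be confounded with dose

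*SAP*

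**What the plan says.** The relevant pieces are spread over several places.

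- **Analysis.** SAP 9.1.3.1: "If data permits, dose proportionality will be assessed using power model for" AUC and Cmax on Day 1 and on Day 15.
- **Population.** SAP 9.1.2: "The primary pharmacokinetic analyses will be based on the Pharmacokinetic population, unless otherwise specified". SAP section 4 defines that population as "All treated subjects for whom a PK sample is obtained and analysed". This covers anyone with an analysed sample, whatever the regimen.
- **Combination group.** SAP 5.1 lists "2mg QD/ATRA 45mg/m 2 /day" as one of eight display groups. It is the only combination group. The other seven are monotherapy, from 1 mg to 20 mg, including the 20 mg PK/PD expansion.
- **Model.** SAP 9.1.3.1 regresses the log PK parameter on log dose, "where a is the intercept and b is the slope", and adds: "Both the intercept and slope will be fitted as fixed effects". There is no ATRA or regimen term.
- **Displays.** Tables 4.3 (Day 1) and 4.4 (Day 15) in SAP Appendix 10 name the Pharmacokinetic population and have empty programming notes. Shell PK_T1 shows one slope per parameter.
- **Other PK models.** Accumulation (9.1.3.2) is analysed by dose cohort, and time invariance (9.1.3.3) separately for each treatment. Dose proportionality is the one PK model that runs across groups.
- **Protocol.** Section 13.8.3.2 calls for the power model and leaves the details to the RAP. Section 1.4.4.2 remarks that "ATRA has only been reported to be an enzyme inducer".

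The SAP drops the PK analysis of ATRA itself (Table 1 and 9.1.1.2). It does not drop the GSK2879552 data of subjects who took ATRA.

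**The concern.** A power-model slope compares exposure at low doses with exposure at high doses. The ATRA subjects all sit at 2 mg, near the bottom of the range, where the documented monotherapy numbers are thin: one subject at 1 mg and two at 2 mg as of 20-NOV-2015 (Protocol 1.3.5). If ATRA lowers GSK2879552 exposure, the low end of the line drops and the slope rises. A drug that is truly dose proportional could then look more than proportional. The fitted line cannot tell an ATRA effect from a dose effect, because the model has no term for the former.

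Whether ATRA changes GSK2879552 exposure is an open question in this study. A Part 1 secondary objective is to characterise GSK2879552 PK both with and without ATRA.

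**Working it through.** The documents give no expected slope, precision or sample size for this analysis, so there is no planned figure to reproduce. The check asks how far the slope moves if ATRA subjects are included without a term.

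**Inputs from the documents**
- Monotherapy numbers at 20-NOV-2015: 1, 2, 7 and 1 at 1, 2, 4 and 8 mg (Protocol 1.3.5).
- First combination cohort: three subjects planned at 2 mg (SAP 2.3). The final number is not given.

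**Assumptions**
- Monotherapy numbers 1, 2, 7, 3, 3, 6 at 1, 2, 4, 8, 12, 20 mg (22 subjects), plus n_A = 3 or 6 on 2 mg + ATRA.
- Exposure ratio R (ATRA versus no ATRA at the same dose) of 0.8 to 0.6, that is, 20-40% lower.
- Between-subject CV 40%, so the log-scale SD is sqrt(ln(1 + 0.4²)) = 0.385.

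**Formula.** With one record per subject, leaving out the ATRA term shifts the slope by

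bias = ln(R) × n_A × (ln 2 − mean ln dose) / Sxx,

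where the mean and Sxx (the sum of squared deviations of ln dose) are taken over all pooled subjects. The 90% half-width is about 1.71 × 0.385 / sqrt(Sxx).

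| | n_A = 3 | n_A = 6 |
|---|---|---|
| Pooled N | 25 | 28 |
| Mean ln dose (geometric mean dose) | 1.793 (6.0 mg) | 1.676 (5.3 mg) |
| Sxx | 20.78 | 24.03 |
| n_A × (0.693 − mean) / Sxx | −0.159 | −0.245 |
| Bias, R = 0.8 (ln R = −0.223) | 0.035 | 0.055 |
| Bias, R = 0.6 (ln R = −0.511) | 0.081 | 0.125 |
| 90% half-width, pooled | 0.145 | 0.134 |

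The shift is therefore between about a quarter (0.035 / 0.145) and nine tenths (0.125 / 0.134) of the half-width. At R = 1 it is exactly zero.

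**Sensitivity to the assumed numbers.** Six other sets of cohort sizes, with 3 to 12 ATRA subjects, put the pooled geometric mean dose at 4.4 to 7.9 mg, always above 2 mg. With a true slope of 1, the pooled slope was:

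- 1.04 to 1.11 at R = 0.7
- 1.08 to 1.21 at R = 0.5
- 0.93 to 0.98 at R = 1.25

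The bias can pass the half-width only with larger effects or more ATRA subjects than in the table above.

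**Check of the remedy.** Take 1/2/7/1/4/6 monotherapy subjects, 6 ATRA subjects, R = 0.7 and a true slope of 1. The pooled fit gives 1.086. Restricting to monotherapy gives 1.000. Adding an ATRA indicator also gives 1.000, with an ATRA coefficient of ln 0.7 = −0.357.

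**Precision after the remedy.** All ATRA subjects share one dose, so once they have their own indicator they carry no information on the slope. Both options therefore rest on the monotherapy Sxx, which is 16.66 for the table's numbers. The half-width is 1.71 × 0.385 / sqrt(16.66) = 0.161.

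**The case against.** Four points on the other side have weight.

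**Pooling is implied, not stated.** A reader might infer that the SAP made a deliberate choice to pool the regimens. It did not say so. The SAP keeps 2 mg + ATRA apart from 2 mg monotherapy in its display groups. Table 1.9 carries an explicit note to include the combination group, while Tables 4.3 and 4.4 say nothing either way, so a programmer could leave it out. This stands as a limit on the wording. But no passage excludes these subjects, so following the plan literally includes them.

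**No ATRA effect is documented.** The enzyme-inducer remark in Protocol 1.4.4.2 supports an argument that ATRA is very unlikely to raise GSK2879552 exposure. It does not report that ATRA lowers it. Protocol 10.2.1 describes almost no metabolic turnover in human microsomes and hepatocytes, which weakens enzyme induction as a route. The same section admits that the clearance mechanism is poorly understood, so an effect is possible but unproven.

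**Day 1 and Day 15 differ.** A reader might apply one bias to all four slopes. Induction needs repeated dosing: Protocol 1.3.6.1 describes ATRA's own concentrations falling over a week of treatment. GSK2879552 Cmax typically occurs within the first hour (Protocol 1.3.4). Day 1 Cmax should be nearly untouched, and Day 1 AUC much less affected than Day 15.

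**Little depends on the result, and the remedy costs precision.** The analysis is descriptive, is run only if data allow, and has no acceptance limits for the slope. Part 2 was not started. PK parameters are also summarised by cohort and listed individually, so a marked ATRA effect could be seen there. At R = 0.8 the root mean squared error of the slope is about the same pooled (0.092 to 0.096) as from monotherapy alone (0.094). The gain in accuracy is clear only for larger effects.

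**Conclusion.** The point holds in conditional form. Read literally, the plan puts the 2 mg + ATRA subjects into a single dose slope with no regimen term, and any ATRA effect on GSK2879552 exposure would be confounded with dose. Induction would push the slope upward, chiefly in Table 4.4.

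The size is 0.035 to 0.125 for a 20-40% exposure loss and 3 to 6 ATRA subjects, which is below the 90% half-width of 0.134 to 0.145. The cohort sizes at 8, 12 and 20 mg, the number of ATRA subjects, the CV and the ATRA effect are all assumed.

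The documents do not support saying that the reported slope will be biased, or that GSK2879552 will be wrongly described as more than dose proportional. That would require an ATRA effect that they neither report nor rule out. Severity is low: this is a cheap improvement to a descriptive analysis.

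**What to change.** State in SAP 9.1.3.1, and repeat in the programming notes of Tables 4.3 and 4.4, one of two options:

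1. Fit the power model to GSK2879552 monotherapy subjects only.
2. Keep the whole Pharmacokinetic population and add an ATRA yes/no fixed effect, reporting the dose slope adjusted for it.

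The slope estimate is the same under both, because the ATRA subjects share one dose. The second option also gives an estimate of the ATRA effect, which bears on the secondary objective of GSK2879552 PK in combination. Using the same choice for Day 1 and Day 15 keeps the two tables comparable, although the need is greater on Day 15.

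The cost is a line of text and either a population filter or one model term. Under the assumptions above, the 90% half-width widens from 0.134-0.145 to about 0.16, an increase of roughly 11-20%.

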#### 9.1.3.2. Accumulation

If data permits, accumulation using ANOVA will be performed for AUC(0- $\tau$ ) on Day 15 vs AUC(0- $\tau$ ) on Day 1 by dose cohort.

To estimate the extent of accumulation after repeat dosing, the observed accumulation ratio (Ro) based on AUC data will be determined as follows:

$$Ro = AUC(0-\tau)_{D15} / AUC(0-\tau)_{D1}$$

Assuming both linear and time-invariant pharmacokinetics, the Ro at steady-state should be unity.

An ANOVA with a random effect term for subject and fixed effect terms for day will be performed by dose on the  $\log_e$ -transformed PK parameters AUC(0- $\tau$ ). Day will be treated as a class variable in the model. The accumulation ratio of GSK2879552 will be estimated by calculating the ratio of the geometric least squares (GLS) means of the PK parameter between Day 15 and Day 1 for all dose levels and the corresponding 90% CI for each ratio.

The accumulation ratio will be summarized by dose.

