1.3.4. Pharmacokinetics of GSK2879552 in Humans

GSK2879552 pharmacokinetics (PK) will be evaluated in a limited number of subjects in the first time in human study in small cell lung cancer patients (GSK study 200858, NCT# 02034123) prior to the initiation of this study. PK of GSK2879552 in human were predicted using in vitro microsomes and hepatocytes data, as well as in vivo intravenous (IV) pharmacokinetic data from mice, rats, and dogs combined with simple allometric scaling and Dedrick transformation. The human blood clearance is predicted to be around 5.4 mL/min/kg for a 70 kg human. The human blood volume of distribution is predicted to be most likely between 1.0 and 1.5 L/kg leading to a range of terminal half-life of 2.1 to 3.2 hours. Based on the good oral bioavailability in animals and the predicted low human clearance, the oral bioavailability is expected to be around 75% to 100% in humans.

As of 20-NOV-2015, the PK of GSK2879552 was evaluated following administration of single (N=18) and repeated (N=16) oral administration of 0.25 mg to 3 mg of GSK2879552 in subjects with SCLC in Study 200858 and following single (N=11) and repeated (N=8) oral administration of 1 mg to 8 mg in subjects with AML in Study 200200. GSK2879552 pharmacokinetics are characterized by a rapid absorption with

maximum concentration occurring typically within the first hour after dosing. GSK2879552 is eliminated slowly with an average terminal phase half-life of 12 to 38 hours, leading to a moderate average increase in exposure of 72% for AUC at 2 mg daily. Following single and repeated administration of 0.25 mg to 4 mg of GSK2879552, C_{max} and AUC tended to increase in a dose proportional fashion.

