- Corticosteroids should be promptly initiated (e.g., 10 mg of dexamethasone every 12 hours until resolution of retinoic acid syndrome). Once resolved the corticosteroid dose can be progressively reduced over 1-2 weeks
- GSK2879552 and/or ATRA may be withheld at the physician's discretion. Due to the long half-life of GSK2879552 (about 16 hours), treatment interruption may not immediately reverse the symptoms of retinoic acid syndrome. If interrupted, GSK2879552 treatment may be reinitiated at the original or a reduced dose, once the signs and symptoms resolve and the patient's clinical condition improves
- In patients with elevated WBC counts, prompt initiation of hydroxyurea is suggested, or treated as per standard local practice (e.g., dose of 2 to 3g PO 2- or 3-times daily for WBC $>30 \times 10^9/L$)
- In cases of severe leukocytosis, use of leukapheresis may be appropriate
- For substantial fluid accumulation, initiation of furosemide may be appropriate, as per local standard practice
- Patients with pericardial effusion (a less common manifestation of retinoic acid syndrome) can require urgent cardiac intervention due to it being a life-threatening condition
- Patients with increasing serum creatinine levels should be evaluated for tumor lysis syndrome
- Patients experiencing a rapid increase in peripheral blood cells should be monitored for disseminated intravascular coagulopathy and hemorrhage
- Imaging techniques such as standard or high-resolution computerized tomography (CT) scan and chest X-ray are useful for establishing a diagnosis of retinoic acid syndrome by identifying pulmonary infiltrates or effusions; noting that a CT scan is more sensitive in detecting early radiological signs of retinoic acid syndrome-associated changes

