### 2.2. Study Objective(s) and Endpoint(s)

Part 1 Objectives	Part 1 Endpoints
Primary Objectives	Primary Endpoints

 
To determine the safety, tolerability, MTD and/or RP2D and regimen of GSK2879552, alone or in combination with ATRA, given orally in adult subjects with AML.
 
	
 
AEs, SAEs, dose limiting toxicities, dose reductions or delays, withdrawals due to toxicities and changes in safety parameters (e.g., laboratory values, vital signs, electrocardiograms [ECGs], physical examinations).
 

Secondary Objectives	Secondary Endpoints

 
To characterize the PK of GSK2879552, alone or in combination with ATRA, after single and repeat-dose oral administration.
 
	
 
GSK2879552 PK parameters following single-(Day 1) and repeat-dose (Day 15) administration of GSK2879552, including AUC, Cmax, tmax, t1/2 (terminal phase and/or effective half-life), accumulation ratio, and time invariance
 

 
To evaluate clinical response after treatment with GSK2879552, alone or in combination with ATRA.
 
	
 
Objective response rate defined as the percentage of subjects achieving complete remission (CR), partial remission (PR), CRp (as per CR but platelet
 

[figure not shown]
Part 1 Objectives	Part 1 Endpoints
	Count <100 x 10  /L) and morphologic leukemia free state per response criteria (Cheson, 2003).

 
To characterize the PK of ATRA in combination with GSK2879552 after single and repeat-dose oral administration.
 
	
 
ATRA PK parameters following single and repeat-dose administration of ATRA and GSK2879552, including AUC, Cmax, tmax, t1/2 (terminal phase).
 

Exploratory Objectives	Exploratory Endpoints

 
To explore markers of differentiation (including morphology) in response to GSK2879552, alone or in combination with ATRA.
 
	
 
Change from baseline expression in cell surface markers in AML cells derived from bone marrow and/or peripheral blood.
 

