#### 9.1.3.3. Time Invariance

To evaluate whether the pharmacokinetics remains unaltered after repeat dosing a similar analysis to that described above will be carried out after  $\log_e$ -transformation of AUC(0- $\infty$ ) for D1 and AUC(0- $\tau$ ) for D15, the difference of which provides the steady-state ratio (Rs).

A mixed effect model will be fitted with day as a fixed effect and subject as a random effect for each treatment (dose) separately. AUC(0- $\tau$ ) on D15 will be compared to AUC(0- $\infty$ ) on D1 in order to assess time invariance for each dose. The Kenward & Roger (KR) degrees of freedom approach will be used. The ratio and 90% confidence interval will be calculated by back-transforming the difference between the least square means for the two days and associated 90% confidence interval, for each dose. Assuming both linear and time-invariant pharmacokinetics, the Rs at steady-state should be one.

The time invariance ratio will be summarized by dose.

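### SAP 9.1.3.2 gives the accumulation ratio Ro an expected value of 1 under linear, time-invariant PK; only Rs has that expected value

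*SAP*

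**What the plan says.** The Part 1 secondary PK endpoint in SAP 2.2 lists half-life, accumulation ratio and time invariance as separate items: "terminal phase and/or effective half-life), accumulation ratio, and time invariance".

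Two ratios serve the last two items:

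- **Ro (SAP 9.1.3.2)** is Day 15 AUC(0-τ) over Day 1 AUC(0-τ). It is estimated by an ANOVA on the log scale and reported as a geometric mean ratio with a 90% CI. The SAP adds: "Assuming both linear and time-invariant pharmacokinetics, the Ro at steady-state should be unity".
- **Rs (SAP 9.1.3.3)** is Day 15 AUC(0-τ) over Day 1 AUC(0-∞). The SAP says: "Assuming both linear and time-invariant pharmacokinetics, the Rs at steady-state should be one".

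SAP 9.1.1.2 introduces both ratios but gives only the second the time-invariance role: it "will be calculated to assess time invariance". Protocol 13.8.3.1 does the same. Neither section gives a reference value for Ro.

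On the drug itself, Protocol 1.3.4 first gives a preclinical prediction, "leading to a range of terminal half-life of 2.1 to 3.2 hours". It then reports human data with an average terminal half-life of 12 to 38 h, "leading to a moderate average increase in exposure of 72% for AUC at 2 mg daily". Protocol 4.8.4.1 uses a half-life of about 16 h.

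**The concern.** The two ratios have the same numerator and different denominators, yet the SAP gives both an expected value of 1 under the same assumptions. Both can be 1 only if Day 1 AUC(0-τ) equals Day 1 AUC(0-∞), that is, if nothing remains at 24 h and the drug does not accumulate. The protocol's human data say otherwise.

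What is at stake is how the results are read. Table 4.5 (accumulation) and Table 4.6 (time invariance) use the same shell, PK_T2. With a common benchmark of 1, a normal Ro near 1.7 beside an Rs near 1 would look contradictory, and ordinary accumulation could be written up as a departure from linear or time-invariant kinetics. SAP 9.1 also allows the PK results to go into a separate report, where the plan's stated reference value may be the reader's only guide.

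**Working it through.** **Inputs**

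- τ = 24 h: once-daily continuous dosing (Protocol 4.1).
- Observed average terminal half-life 12 to 38 h; AUC increase of 72% at 2 mg daily (Protocol 1.3.4).
- Half-life of about 16 h (Protocol 4.8.4.1).
- Preclinically predicted half-life 2.1 to 3.2 h (Protocol 1.3.4).

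**Step 1. The identity, with no compartment model.** By superposition, linear and time-invariant kinetics give steady-state AUC(0-τ) = single-dose AUC(0-∞). Hence

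- Rs = AUC(0-τ) at steady state / Day 1 AUC(0-∞) = 1
- Ro = AUC(0-τ) at steady state / Day 1 AUC(0-τ) = Day 1 AUC(0-∞) / Day 1 AUC(0-τ), which is above 1 whenever drug remains at 24 h.

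**Step 2. Size.** With mono-exponential decline, Ro = 1 / (1 − 2^(−24/t½)).

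| Half-life | Source | Expected Ro |
|---|---|---|
| 2.1 h | preclinical prediction, lower | 1.000 |
| 3.2 h | preclinical prediction, upper | 1.006 |
| 5.5 h | point at which Ro reaches 1.05 | 1.05 |
| 12 h | observed, lower | 1.33 |
| 16 h | Protocol 4.8.4.1 | 1.55 |
| 38 h | observed, upper | 2.82 |

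The SAP's value of 1 is reproduced, to a close approximation, at the superseded preclinical half-life. It is not reproduced at any half-life reported in humans.

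**Step 3. The reported 72%.** If this increase is Day 15 over Day 1 AUC(0-τ), Ro is about 1.72. Inverting the formula, t½ = 24 × ln 2 / ln(1.72/0.72) = 19.1 h. That lies inside the observed range, so the figure fits linear kinetics.

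**Step 4. Is Day 15 at steady state?** After 15 daily doses at t½ = 38 h, the fraction reached is 1 − 2^(−15×24/38) = 0.9986. Superposing 15 doses in a one-compartment oral model (absorption rate 3/h, assumed) gives:

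| Half-life | Ro | Rs |
|---|---|---|
| 12 h | 1.342 | 1.000 |
| 16 h | 1.559 | 1.000 |
| 38 h | 2.848 | 0.999 |

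Withholding Days 2 and 3, as Protocol 4.2.4 allows, still gives Rs 0.996 at 38 h. Failure to reach steady state does not rescue the sentence.

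**Step 5. Multi-phase decline.** Let a fraction f of AUC(0-∞) lie in a 38 h phase and the rest in a 4 h phase (f and the 4 h phase are assumptions). Then Ro = 1 / [(1 − f)(1 − 2^(−24/4)) + f(1 − 2^(−24/38))]. This gives 1.26 at f = 0.3, 1.49 at 0.5, 1.84 at 0.7 and 2.82 at 1. The size depends on the model; the direction does not.

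**Step 6. Would a 90% CI exclude 1?** Lower limit = 1.72 / exp(t(n−1, 0.95) × SD/√n), with an assumed SD of the log ratio:

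| n | SD 0.2 | SD 0.3 | SD 0.5 |
|---|---|---|---|
| 2 | 0.70 | 0.45 | 0.18 |
| 4 | 1.36 | 1.21 | 0.96 |
| 8 | 1.50 | 1.41 | 1.23 |

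In the smallest cohorts the interval would include 1 regardless. With about 4 subjects or more it would often exclude 1 even though the kinetics are linear and time-invariant.

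**The case against.** The best case on the other side accepts that the sentence is wrong and argues that it hardly matters. The stated purpose of Ro is to estimate the extent of accumulation. No comparison with 1 is planned, and the PK_T2 shell shows no reference value. The tables are titled separately, and Protocol 1.3.4 already attributes the AUC increase to slow elimination. The analysis is descriptive, runs only if data permit, and belongs to an abbreviated report of a terminated study. The sentence looks like the Rs statement carried over by mistake. All of this stands, and it limits the point to interpretation.

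The numerical criticisms also stand in part:

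- Protocol 1.3.4 does not define the 72% as Day 15 over Day 1 AUC(0-τ), and it describes data from two studies. The 1.72 and the 19 h are inferences.
- The value 2.82 puts a terminal half-life into a one-compartment formula.
- The CI table rests on assumed SDs and cohort sizes. At the 20-NOV-2015 cutoff, repeat-dose PK existed for 8 AML subjects across all doses. A one-subject cohort gives no CI.
- Routine Day 1 sampling ends at 24 h (Protocol Table 3, footnote 1). In the one-compartment approximation, the share of AUC(0-∞) that must be extrapolated is 2^(−24/12) = 25% at 12 h and 2^(−24/38) = 65% at 38 h. Day 1 AUC(0-∞)/AUC(0-τ) is therefore an imprecise benchmark in practice, and comparing Ro with it is algebraically the same as comparing Rs with 1. This favours simple deletion.

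None of this makes unity the right value for Ro, and no other section corrects the sentence.

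**Conclusion.** The concern holds. The SAP's stated expectation for Ro is incorrect; the expectation for Rs is correct. The identity in Step 1 rests only on linearity, time invariance and Day 15 being at steady state, and the last is met to within 0.2% at the longest reported half-life with uninterrupted daily dosing. The expected values of 1.33 to 2.82 also assume mono-exponential decline and are indicative.

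The consequence is confined to how a named secondary PK result is read. The Ro estimate, its CI, the Rs analysis and the power model are unaffected, and no sample size or decision rule depends on Ro = 1. It is worth correcting before reporting because the stated benchmark would turn normal accumulation into an apparent kinetic anomaly.

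**What to change.** Delete the unity sentence from SAP 9.1.3.2. If a reference is wanted, replace it with:

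> Under linear, time-invariant pharmacokinetics, Ro is expected to equal Day 1 AUC(0-∞)/AUC(0-τ); only Rs (Section 9.1.3.3) is expected to be 1.

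If the replacement is used, note beside it how much of Day 1 AUC(0-∞) is extrapolated. Continue to judge time invariance on Rs and dose proportionality on the power model, as already planned. The cost is one sentence; models, tables and data do not change.
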